**Table 1: Schedule of Assessments and Procedures**

Measures	Acclimation	BL	Heat
Run Time (min)	30	15	120
Cumulative Time (min)	30	45	165
*Tcore		††	††
Skin Temperatures		††	††
*Sweat Rate		1x	4x
Thermal Sensation	1x	2x	12x
Thermal Comfort	1x	2x	12x
Laser Doppler Flow		2x	6x
Brachial BP, O 2 sat		2x	12x

†† Tcore and skin temperature measurements will be monitored and collected simultaneously throughout the study. \*Tcore and Sweat Rate in persons with Hi-SCI only.

obtained during BL and Thermal Challenge for all visits (**Table 1**). *Tcore*: will be monitored by a disposable forehead skin temperature sensor (Bair Hugger™ Spot On™ Temperature Monitoring System, 3M, Maplewood, Minnesota) in persons with Hi-SCI only. *Skin Temperature (Tsk)*: will be monitored using TX-4 Skin Surface probes and Iso-Thermex Multichannel Thermometer (Columbus Instruments, Columbus, OH). Skin thermocouples will be taped to 12 sites on the anterior and dorsal trunk of the participant. *Microvascular Perfusion (LDF)*: will be measured using laser probes on the skin of both ventral forearms and calves with a Periflux System 5000 Laser Doppler (Perimed, Stockholm, Sweden) for calculation of CVC. *Sweat rate (SR)*: will be measured by the Quantitative Sweat Measurement System (WR Medical Electronics, Stillwater, MN) with capsules secured to 4 sites: left upper arm, left forearm, left mid-thigh, and left midcalf.

**Thermal Sensation (TS) and Thermal Comfort (TC):** TS will be measured by a 9-point thermal sensation scale, while TC will be measured by a 6-point thermal comfort scale (attached). Tympanic temperature will be assessed in all participants using a Braun PRO 6000 infrared ear thermometer (Welch Allyn, Skaneateles Falls, NY).

**Hemodynamic Measurement Procedures:** Brachial BP: BP will be measured at the brachial artery using the Carescape Dinamap V100 Automated BP Monitor (Carescape, Milwaukee, WI). BP will be obtained at 10-minute intervals throughout BL and Thermal Challenge and immediately pre and post LDF measurement for calculation of CVC.

**Sample Size and Statistical Approach:** We are hypothesizing that after 2 hours of heat exposure, the average increase in Tcore of persons with Hi-SCI with the wet cooling vest will be  $0.3 \pm 0.3^{\circ}\text{C}$  compared to an increase of  $0.6 \pm 0.3^{\circ}\text{C}$  (data from our prior study using an identical heat challenge, but with no vest). Therefore, a sample size of 10 participants would be needed to achieve a power of 81% for a two-sided, one-sample analysis at an alpha of 0.05. For Phase I (safety), descriptive statistics will be used to determine the number of participants who have a vest failure. Vest failure will be defined as any area of skin under the vest (Tsk) with a temperature  $<20^{\circ}\text{C}$  and/or the number of participants who report a TS of “cold” or “very cold”. For efficacy testing, a 2 x 2 (condition, time) repeated measures ANOVA will be used to determine significant main or interaction effects. If main or interaction effects are determined, post hoc analysis will be performed using t-tests or appropriate non-parametric tests to determine significant differences between conditions. Significance will be set at an alpha level of 0.05.

3a. Basic Information - Even if described under “Procedures”, list the following information, where pertinent:

3a. i) Procedures to be used (e.g., biopsy, surgical operation, interview, experimental diet, infusion, drug administration, etc.) and with what frequency?

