**2. Thermal Challenge with Wet Cooling Vest vs. No Vest (Phase 2; 2 visits, participants with Hi-SCI only):** After 15 minutes of baseline data collection in a thermoneutral environment (25°C), participants with HI-SCI will be fitted with an appropriately sized cooling *wet vest* or will wear *no vest* (in random order). To provide evaporative heat loss, the vest material will be saturated with water using a spray bottle. Participants will then be transferred into a warm (35°C, 35% relative humidity) thermal chamber for up to 2 hours. Tcore (Bair Hugger™ Spot On™ forehead skin sensor ) and Tsk (thermocouples at multiple sites under the vest and on hands and feet) will be measured continuously; subjective TS and TC will be measured at 10-minute intervals; LDF will be measured as above (for CVC) at 20-minute intervals. SR will be measured for 15 minutes every 30 minutes (4 times). HR, BP, blood oxygen saturation, and tympanic temperature will be measured at 10-minute intervals for vital signs' information. Participants will be queried if they have any feelings of discomfort. If the participant's Tsk underneath the vest falls below 20°C, or Tcore rises to 38°C, and/or the participant requests study termination because of discomfort, the vest will be removed, the heat challenge will be immediately terminated, and the participant will be transferred to a cool environment, covered with cool blankets, as appropriate, and provided cold liquids. The study physician will be directly responsible for subjects' medical safety during study protocols. Subjects' Tcore, HR and BP, will be monitored at frequent intervals. Symptoms suggestive of AD or hyperthermia will be assessed every 10 minutes. The study physician will be notified immediately of any symptoms or signs of concern. Subjects will be medically evaluated promptly, and the study terminated if any safety issues arise. Subjects will be monitored for at least 30 minutes of recovery to ensure Tcore returns to within 1% of BL value.

**Determinants of Efficacy Failure or Success for Phase 2:** 65% of participants in the *wet vest* condition will have a significantly reduced elevation in Tcore ( $\leq 0.3^{\circ}\text{C}$ ), and 2) a greater percentage will report increased thermal comfort (decreased perception of feeling “hot”, “very hot”, or “uncomfortable”) compared to the expected increase in Tcore of  $0.6^{\circ}\text{C}$  and reported thermal comfort in the *no vest* condition.

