**Outcome Variables:** **Phase 1:** Skin thermocouple temperatures, ratings of thermal comfort and sensation, cold spots, and any reported physical discomfort from the vest. **Phase 2:** The primary endpoint will be the magnitude and rapidity of the rise in Tcore upon exposure to a warm environment. The perception of thermal comfort and sensation of heat will be obtained as secondary endpoints.

**Procedures: Thermoregulatory Measurement Procedures:** The following measurements will be

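### The efficacy analysis names no deciding result: any effect in the 2 x 2 ANOVA, including time, opens unadjusted tests between conditions, although only the condition-by-time interaction tests a difference in the rise in Tcore

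*Combined protocol and SAP*

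**What the plan says.** Outcome Variables defines the Phase 2 target: "The primary endpoint will be the magnitude and rapidity of the rise in Tcore". Research Design likewise looks for a smaller rise with the vest than without it in the same participants.

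The Sample Size and Statistical Approach paragraph frames the hypothesis as a change: "We are hypothesizing that after 2 hours of heat exposure, the average increase in Tcore of persons with Hi-SCI" is expected to be 0.3 ± 0.3°C with the vest, against 0.6 ± 0.3°C from a prior study without one. It concludes that "a sample size of 10 participants would be needed to achieve a power of 81% for a two-sided, one-sample analysis".

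The same paragraph then turns to a different analysis. A 2 x 2 (condition, time) repeated measures ANOVA will look for main or interaction effects, and "If main or interaction effects are determined, post hoc analysis will be performed using t-tests or appropriate non-parametric tests", with alpha 0.05 throughout. It does not identify the two times, the post hoc contrast or the deciding term.

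The section on the Phase 2 thermal challenge places the 15-minute baseline before the vest is fitted.

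**The concern.** With times read as baseline and end of heat (the natural reading, since the hypothesis is an average increase after 2 hours), the terms of the ANOVA answer different questions:

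- **Interaction:** the difference between conditions in the rise. This is the hypothesis.
- **Condition main effect:** averages in a value taken before the vest was on, so an expected 0.3°C effect is halved to 0.15°C.
- **End-of-heat comparison:** compares final temperatures and ignores baseline differences between visits.
- **Time:** shows that the chamber warms people, whatever the vest does.

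The plan gives all of them the same standing: any one opens the tests between conditions. An analyst could therefore report efficacy from one result while another, from the same 10 participants, is not significant. The Significance section makes a full funding application depend on efficacy.

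**Working it through.** **Inputs from the plan:** rise 0.6°C without and 0.3°C with the vest, SD of a rise 0.3°C, n = 10, two-sided alpha 0.05.

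**Assumed, not in the documents:** correlation ρ between a participant's two rises, 0 to 0.75; visit-to-visit within-person SD of baseline Tcore, s = 0.1 to 0.3°C; and the share k of a visit's baseline deviation that persists to end of heat.

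With two conditions and two times, each term is a one-sample t-test on a within-person contrast. Power comes from the noncentral t with 9 df and noncentrality d√10, where d = mean/SD of the contrast.

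**1. The plan's figure.** d = 0.3/0.3 = 1 gives 80.3%, in line with the stated 81%.

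**2. Interaction.** SD of the paired difference in rise = 0.3√(2(1−ρ)).

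| ρ | SD | Power |
|---|---|---|
| 0 | 0.424 | 51.4% |
| 0.25 | 0.367 | 63.4% |
| 0.5 | 0.300 | 80.3% |
| 0.75 | 0.212 | 97.7% |

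The plan's figure carries over to this test only near ρ = 0.5.

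**3. Time.** SD of a participant's mean rise = 0.3√((1+ρ)/2), which is 0.260 at ρ = 0.5. If the vest does nothing, d = 0.6/0.260 = 2.31 and power exceeds 99.9%. If it works as hoped, d = 0.45/0.260 = 1.73 and power is 99.8% (99.4% at ρ = 0.75). The post hoc tests are opened almost surely either way.

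**4. Other terms at ρ = 0.5.** Holding the paired-difference variance at 0.09:

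- End of heat: effect 0.3, variance 0.09 + 2s²(2k−1).
- Condition main effect: effect 0.15, variance 0.0225 + 2ks².

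*Full carry-over (k = 1):*

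| s | End-of-heat variance | Power | Condition variance | Power |
|---|---|---|---|---|
| 0.1 | 0.110 | 72.1% | 0.0425 | 53.7% |
| 0.2 | 0.170 | 53.7% | 0.1025 | 26.4% |
| 0.3 | 0.270 | 37.2% | 0.2025 | 15.7% |

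*Half carry-over (k = 0.5):* the end-of-heat variance is 0.09 for any s, so its power is 80.3%, equal to the interaction. The condition variance is 0.0225 + s², giving 65.0%, 39.6% and 24.5% for s = 0.1, 0.2 and 0.3.

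*No carry-over (k = 0):* the end-of-heat variance is 0.09 − 2s². This is 0.07 at s = 0.1 (89%) and 0.045 at s = 0.15 (98%). The condition main effect has d = 0.15/0.15 = 1, so 80.3%.

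With s = 0 all three tests have the same power.

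**5. Error with no vest effect.** Simulation, 60,000 trials per setting, ρ = 0, 0.5, 0.75 and s = 0.1, 0.2, 0.3, with full carry-over:

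- Any single test: about 5%.
- Interaction or condition counted as success: about 8.0 to 9.8%.
- Adding the end-of-heat test that time opens: about 8.2 to 10.6%, an increment of 0.2 to 1.0 point.
- Any of the three, in the direction favouring the vest: about 4 to 5.3%, against 2.5% for one test.

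**6. Disagreement with a true 0.3°C effect.** In the same simulation, the interaction and end-of-heat verdicts differ in about 13 to 47% of trials at ρ = 0.5, and in 8 to 55% over ρ from 0 to 0.75.

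**The case against.** The strongest reply is that the target is already clear. The secondary objective, Research Design, Outcome Variables and the hypothesis sentence all speak of change in Tcore, and a sensible analyst would look at the interaction. The Phase 2 section also has its own success rule, that 65% of participants in the wet vest "condition will have a significantly reduced elevation in Tcore". This narrows the ambiguity but does not remove it. The analysis paragraph still puts main effects on the same footing, and the 65% rule is not an ANOVA result.

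Four stronger readings are tempting, and the documents do not support them:

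- *The plan has 8 to 10.6% error.* That requires any of three results to count as success. The plan does not say so; it only fails to exclude it.
- *The screening step inflates error.* It is ineffective but nearly harmless, because the end-of-heat test it opens keeps 5% error on its own.
- *The alternatives have much less power.* That needs baseline differences to carry fully into the end value. With half carry-over the end-of-heat test matches the interaction, and with none it does better. The documents do not say which applies.
- *Naming the interaction secures about 80% power.* That holds only near ρ = 0.5. The plan's 81% was computed for a one-sample analysis, with the 0.6°C taken from a prior study, and not for an ANOVA term.

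It is also fair that efficacy is the secondary objective, behind safety, in an exploratory proof-of-concept study. The value to use when a visit stops early, the analysis of rapidity and the link to the 65% rule are separate gaps and do not bear on this point.

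**Conclusion.** The point stands as a defect in the decision rule. The plan lets an effect unrelated to the vest, and almost certain to appear, open unadjusted tests between conditions, and it does not say which result decides. The case for the interaction is that it is the term that tests the stated hypothesis; it does not rest on superior power in every setting.

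The opening step alone adds at most about 1 point of error. Two-sided error of about 8 to 10.6% arises only if any of three results may count. That figure, and the 37 to 72% (end of heat) and 16 to 54% (condition) power against 80% for the interaction, assume baseline SDs of 0.1 to 0.3°C with full carry-over; the power figures also assume ρ = 0.5. Reading the two times as baseline and end of heat is an inference from the hypothesis sentence. Severity is modest: this should be fixed because fixing it is nearly free.

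**What to change.** Add to the Sample Size and Statistical Approach paragraph:

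*The efficacy test for the magnitude of the rise in Tcore is the condition-by-time interaction with time = baseline and end of heat, i.e. the paired comparison of change from baseline, wet vest minus no vest, at two-sided alpha 0.05, with the Wilcoxon signed-rank test as a sensitivity analysis. Main effects and single-time comparisons are descriptive.*

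State beside the sample size that the 81% applies to this test only if the SD of the paired difference is 0.3°C (ρ about 0.5), and that power with 10 participants is 51% at ρ = 0 and 98% at ρ = 0.75.

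The cost is two or three sentences. No participants, visits or measurements are added, and the interaction is already part of the planned ANOVA.

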## Procedures

**Thermoregulatory Measurement Procedures:** The following measurements will be obtained during BL and Thermal Challenge for all visits (**Table 1**).

*Tcore*: will be monitored by an disposable forehead skin temperature sensor(Bair HuggerTM Spot OnTM Temperature Monitoring System, 3M, Maplewood, Minnesota)in persons with Hi-SCI only.

In all participants:

*Skin Temperature (Tsk)*: will be monitored using TX-4 Skin Surface probes and Iso-Thermex Multichannel Thermometer (Columbus Instruments, Columbus, OH). Skin thermocouples will be taped to 12 sites on AB controls and 14 sites – 10 sites on the chest/abdomen (five on each side) and 4 sites on the bilateral hands and feet (2 on each side) on persons with Hi-SCI.

*Sweat rate measurement (QS)*: will be measured for 15 minutes, once during the baseline period and 4 times during the thermal challenge at 30-minute intervals, for a total of 5 measurements.

*Microvascular Perfusion (LDF)*: will be measured using laser probes on the skin of both ventral forearms and calves with a Periflux System 5000 Laser Doppler (Perimed, Stockholm, Sweden) for calculation of CVC.

*Thermal Sensation (TS) and Thermal Comfort (TC)*: TS will be measured by a 9-point thermal sensation scale, while TC will be measured by a 6-point thermal comfort scale.

*Tympanic temperature* will be assessed using a Braun PRO 6000 infrared ear thermometer (Welch Allyn, Skaneateles Falls, NY).

## Hemodynamic Measurement Procedures:

*Brachial BP*: BP will be measured at the left brachial artery using the Carescape Dinamap V100 Automated BP Monitor (Carescape, Milwaukee, WI). BP will be obtained at 10-minute intervals throughout BL and Thermal Challenge.

*Blood Oxygen Saturation*: Blood oxygen saturation will be recorded every 10 minutes.

3a. ii) Description of procedures. If pharmacologic agents or radioisotopes are to be administered, provide dosages, mode of administration and duration of usage.

*Core temperature measurement (Tcore)*: will be monitored by an disposable forehead skin temperature sensor, (Bair HuggerTM Spot OnTM Temperature Monitoring System, 3M, Maplewood, Minnesota) in persons with Hi-SCI only.

*Skin temperature measurement (Tsk)*: will be monitored using TX-4 Skin Surface probes and Iso-Thermex Multichannel Thermometer (Columbus Instruments, Columbus, OH). Skin thermocouples will be taped to 12 sites under the vest on the anterior and dorsal trunk of AB participants on AB controls and 14 sites – 10 on the anterior and dorsal trunk and 4 on both hands and feet- on persons with Hi-SCI.

*Microvascular Perfusion (LDF)*: will be measured using laser probes on the skin of both ventral forearms and calves with a Periflux System 5000 Laser Doppler (Perimed, Stockholm, Sweden) for calculation of CVC.

*Sweat rate (SR)*: will be measured by the Quantitative Sweat Measurement System (WR Medical Electronics, Stillwater, MN) with capsules secured to 4 sites: left upper arm, left forearm, left mid-thigh, and left midcalf (C5, T1, L3, and L5 dermatomes, respectively).

*Brachial BP & HR*: will be measured at the brachial artery using the Carescape Dinamap V100 Automated BP Monitor (Carescape, Milwaukee, WI) placed above the left elbow.

*Thermal Sensation (TS)*: TS will be measured by a 9-point thermal sensation scale (attached).

*Thermal Comfort (TC)*: TC will be measured by a 6-point thermal comfort scale (attached).

*Tympanic temperature* will be assessed using a Braun PRO 6000 infrared ear thermometer (Welch Allyn, Skaneateles Falls, NY), along with other vital signs, e.g., BP, HR, O2 sat.

3a. iii) Population to be studied, listing basis for selection or exclusion and number to be studied.

**Participants:** Ten participants with high-level SCI (Hi-SCI: >T6) and 5 able-bodied (AB) participants matched for age ( $\pm 5$  years) and gender will be recruited for study participation. All subjects will be studied at the James J. Peters VA Medical Center, Bronx, NY.

**Participant Recruitment:** Patients referred by their physician following routine physical examinations will be approached for potential study enrollment. Physicians will be informed of the inclusion and exclusion

criteria and will be able to assure us that the patient is an appropriate study participant and that he/she is willing to speak with the study coordinators.

1. Veterans with SCI responding to IRB-approved articles in lay publications and advertisements.
2. Veterans with an ongoing relationship with our center (Metabolic, Pulmonary, or GI SCI clinics).

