**Exclusion Criteria:**

1. known cardiovascular, kidney or untreated thyroid disease
2. traumatic brain injury (mod-severe)
3. diabetes mellitus
4. acute illness or infection
5. broken, inflamed, or otherwise fragile skin
6. pregnancy
7. BMI  $>30 \text{ kg/m}^2$
8. smoking

**Methods:** On 3 separate days (Phases 1 & 2), participants will arrive in the laboratory between 8:00-11:00 AM.

**Preparation for Study Visits:** Participants will be instructed to avoid caffeine and alcohol, maintain normal salt and water intake, and avoid strenuous exercise for 24 hours prior to study on each visit. Participants will wear a T-shirt and shorts during all visits to maximize skin exposure to the warm temperature. The T-shirt will also prevent the cooling vest from directly touching the skin. Each participant will be instructed to eat a light meal (plain bagel or 2 pieces of toast) 2 hours prior to their visit. Participants will be asked to empty their bladders prior to the study visit and again upon arrival, if necessary.

**Instrumentation:** (*For all participants*) After obtaining informed consent, participants will be instrumented in a thermoneutral room ( $25^{\circ}\text{C}$ ) and in their wheelchair (Hi-SCI) or a provided wheelchair for AB controls. Participants will remain seated and relatively still but will be instructed to use their pressure relief seat cushion (e.g., Roho) and maintain their usual pressure relief schedule (e.g., weight shifting every 15 minutes). Laser Doppler flowmetry (LDF) will be used to measure changes in microvascular perfusion rate by placing a Doppler probe on the skin of the ventral forearm and calf bilaterally as an index of vascular sympathetic withdrawal. Changes in skin blood flow will be assessed from calculations of cutaneous vascular conductance (CVC = LDF/MAP), a more accurate measure of change in skin blood flow. An automated blood pressure cuff will be placed above the elbow to measure brachial blood pressure (BP) and heart rate (HR). Sweat rate (SR) will be measured by the Quantitative Sweat Measurement System (WR Medical Electronics, Stillwater, MN) with capsules secured to 4 sites: left

upper arm, left forearm, left mid-thigh, and left midcalf (C5, T1, L3, and L5 dermatomes, respectively). A pulse oximeter will be placed on the second digit to detect blood oxygen saturation. An infrared ear thermometer will be used to assess tympanic temperature.

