**For AB participants (Visit 1):** Skin thermocouples will be secured at 12 sites on the ventral and dorsal torso (mid-clavicular line from T3 to T10 dermatomes, bilaterally) for collection of skin temperatures (Tsk).

**For participants with Hi-SCI (Visits 2 & 3):** Participants with Hi-SCI will be asked to empty their bladders to minimize risk of AD during the heat stress protocols (*wet vest, no vest*). Skin thermocouples will be secured at 14 sites, 10 skin thermocouples on the ventral and dorsal torso (five on each side) and 4 additional thermocouples on both hands and feet (2 on each side) for distal skin temperatures as an indirect index of sympathetic vasomotor regulation. A disposable forehead skin temperature sensor (Bair Hugger™ Spot On™ Temperature Monitoring System, 3M, Maplewood, Minnesota) will be placed on the orbital bone, above the eyebrow, on whatever side is most comfortable for the participant in order to measure core temperature (Tcore).

**Baseline Collection (BL):** (for all 3 Visits) At the end of the instrumentation period (~30 minutes) at 25°C while seated and wearing only shorts and a standard T-shirt, a baseline (BL) collection of the following parameters will be performed for 15 minutes. Tcore (in persons with Hi-SCI only) and Tsk will be measured continuously. Subjective ratings of thermal sensation, assessed on a 9-point scale (TS) and general thermal comfort on a 6-point scale (TC). HR, BP, blood oxygen saturation, tympanic temperature and 5 minutes of LDF will be measured at 10-minute intervals. BP will be assessed immediately pre and post each LDF interval for calculation of CVC. SR will be measured for 15 minutes continuously.

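### The blood-pressure cuff shares the left arm with two sweat capsules and one forearm Doppler probe and inflates just before each Doppler recording; a right-arm cuff would be a cheap improvement to these supporting measures

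*Combined protocol and SAP*

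**What the plan says.** **Cuff.** Section 3a. i), Hemodynamic Measurement Procedures, states "BP will be measured at the left brachial artery". Section 3a. ii), Brachial BP & HR, has the cuff "placed above the left elbow". Section 3, Instrumentation, says "An automated blood pressure cuff will be placed above the elbow" and gives no side, and the hemodynamic paragraph after Table 1 gives none either. Left is thus the only side the plan names, and nothing contradicts it.

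**Sweat capsules.** Section 3a. ii) has "capsules secured to 4 sites: left upper arm, left forearm, left mid-thigh, and left midcalf". Section 3, Instrumentation, lists the same sites.

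**Doppler probes.** Instrumentation describes "placing a Doppler probe on the skin of the ventral forearm and calf bilaterally", and Section 3a. ii) has "laser probes on the skin of both ventral forearms and calves".

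**Timing.** Under Baseline Collection: "BP will be assessed immediately pre and post each LDF interval for calculation of CVC". The hemodynamic paragraph after Table 1 extends this to the thermal challenge, asking for pressure every 10 minutes and also "immediately pre and post LDF measurement for calculation of CVC". The shorter version in Section 3a. i) mentions only the 10-minute readings.

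**Role of the measures.** Instrumentation presents LDF as an index of sympathetic withdrawal in the vessels and defines CVC as LDF/MAP. Outcome Variables makes the rise in core temperature the Phase 2 primary endpoint, with thermal comfort and heat sensation secondary.

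The plan gives no wait after deflation, no pause in sweat collection, no rule for cuffed-side readings, and no statement of how the two forearm probes are combined.

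**The concern.** A cuff above the elbow briefly interrupts flow to everything below it. The left-forearm probe lies below it, and the plan asks for an inflation directly before every recording from that probe. Whatever follows deflation then falls at the start of the recording and has a mechanical rather than a sympathetic cause, in a measure meant to index sympathetic control. The same limb carries both upper-limb sweat capsules, and pressure is taken while sweat is being collected.

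What is at stake is the quality of the mechanistic data. Section 4, Preliminary Studies, describes an earlier study in which the 13 of 20 participants with high-level injury who had lower blood pressure and sweat rate than controls also had the larger core-temperature rise. Measures of this kind are what a reader would turn to when interpreting a result in ten participants, so avoidable noise in them is worth removing.

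**Working it through.** No sample size, power or error-rate figure bears on this point. The check sets the sites side by side and then lays out the schedule.

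**1. Sites on the cuffed limb**
- Sweat capsules: left upper arm and left forearm, so 2 of 4. The other two are on the left leg, so these are the only upper-limb sites.
- LDF probes: two forearms and two calves. One of the 4 probes, and one of the 2 forearm probes, is below the cuff.

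**2. Counts from Table 1**
- Pressure in heat: 120/10 = 12, as tabulated.
- LDF in heat: 120/20 = 6, as tabulated; with 2 at baseline, 2 + 6 = 8 per session.
- Sweat collections: 1 + 4 = 5, each of 15 minutes.

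**3. LDF against inflations**
A pressure reading is required directly before each recording, so 8 of 8 left-forearm recordings per session follow an inflation upstream of the probe.

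**4. Sweat against inflations**
- Readings come every 10 minutes and a collection lasts 15. Since 15 > 10, every collection contains at least one routine inflation, however the clocks are aligned.
- Illustration, with everything starting at minute 0 of heat: pressure at 0, 10, …, 110; LDF from 0 to 5, 20 to 25, …, 100 to 105. The starts coincide with routine readings and the six ends do not, so there are 12 + 6 = 18 inflation times. The four sweat windows (0–15, 30–45, 60–75, 90–105) each hold 3 inflations counting their edges, and 2, 1, 2 and 1 strictly inside.
- Baseline: two 5-minute recordings 10 minutes apart fill 0–5 and 10–15. Bracketing readings fall at 0, 5, 10 and 15, so 4 inflations fall in or at the edges of the 15-minute sweat collection.

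**5. Possible size**
The documents give no inflation time, rebound size or recovery time. As an assumption, let the disturbance last *t* seconds of a 5-minute (300 s) recording. The share affected is *t*/300:

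| Assumed duration | Share of left-forearm recording |
|---|---|
| 30 s | 30/300 = 10% |
| 60 s | 60/300 = 20% |
| 120 s | 120/300 = 40% |

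This is the share of time, not the error in CVC. The error also depends on how far flow departs from its steady level, which the documents do not give.

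**The case against.** The strongest reply is that nothing the trial concludes rests on these measures. CVC and sweat rate are not among the Phase 2 endpoints, are not in either phase's success criteria, and are not named in Sample Size and Statistical Approach. No subgroup analysis by sweat rate is planned, and the earlier study separated its groups by blood pressure and sweat rate, not by CVC. Each participant serves as his or her own control under the same cuff schedule, in random order, so part of any disturbance should cancel. The right forearm, both calves and both leg capsules are untouched. All of this stands and keeps the point small. Cancellation does not, however, protect absolute CVC, left–right or forearm–calf comparisons, and it does not remove noise.

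The remedy can also be challenged. An uncuffed forearm probe already exists on the right, so using that probe alone would serve perfusion equally well, and moving the cuff only shifts the suspected disturbance to the other forearm. That is correct for perfusion. The extra gain from relocation is that it clears the sweat capsules, where the case for a disturbance is weaker.

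A reader might infer more than the documents support:
- **That an artefact enters a forearm average.** The plan does not say the two probes are averaged, so this is conditional.
- **That CVC is inflated.** Neither the size nor the direction of a net error can be derived.
- **That sweat readings are shown to be disturbed in every session.** Inflations fall within the collections, but an effect on collected sweat is not shown. Table 1's footnote also limits sweat rate to participants with spinal cord injury, while the Phase 1 text measures it in able-bodied participants.
- **That cuff and upper-arm capsule physically clash.** Their positions are not given precisely enough to say.

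**Conclusion.** The layout and timing are as described, and the plan offers no mitigation. All 8 left-forearm LDF recordings per session directly follow an inflation upstream of the probe, and every 15-minute sweat collection includes at least one inflation on the limb that holds both upper-limb capsules. This can add a non-sympathetic disturbance to left-forearm CVC and, less certainly, to the upper-limb sweat readings. That consequence is an inference from placement and timing. It assumes that the cuff is on the left as Sections 3a. i) and ii) state, and that *immediately* leaves no meaningful recovery time.

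The point is minor. It concerns supporting mechanistic measures, in both conditions alike, and gives no reason to doubt the core-temperature, comfort or sensation results.

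**What to change.** Specify the right arm for the cuff in Section 3 (Instrumentation, and the hemodynamic paragraph after Table 1), Section 3a. i) (Hemodynamic Measurement Procedures) and Section 3a. ii) (Brachial BP & HR). This clears all four sweat capsules, which are all on the left. State that forearm CVC is calculated from the uncuffed left probe with MAP from the right arm, and that right-forearm LDF is kept as descriptive. That sentence also settles which forearm signal is used. Taking MAP from the opposite arm needs no new kind of assumption: the plan already divides right-forearm flow by a left-arm pressure.

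The change needs no equipment and no session time. The downside is that forearm CVC rests on one probe instead of two.
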